### **Ophthalmologic Assessments:**

Since approval of vigabatrin for the treatment of infantile spasms in 2009, the FDA has required a risk evaluation and mitigation strategy (REMS) that includes recommended ophthalmologic evaluations every 3 months. For the current study, this recommended safety guidelines of the REMS program will be followed, but we recognize that this creates some unique challenges within a double-blinded, placebo-controlled randomized study. All subjects enrolled in the PREVeNT Trial will follow a standard ophthalmologic protocol.

At each site, the ophthalmologic examination will be completed by a pediatric ophthalmologist or neuro-ophthalmologist who has experience in TSC infant ophthalmologic examinations.

The protocol will include a baseline eye exam within 4 weeks of initial enrollment in study. This will include: visual acuity, pupillary reaction and dilated funduscopy examination with fundus photography. Electroretinography (ERGs) will **not** be obtained as part of the ophthalmologic examination at any of the participating sites. It should be noted that the FDA risk evaluation and mitigation strategy (REMS) program does not require ERGs.

Subjects randomized to the Blinded Treatment phase (Arm A) will be treated with vigabatrin 100mg/kg/day or placebo until 24 months of age, or have a clinical seizure or electrographic seizure on EEG as determined by the Central EEG Reader. During this phase of the study, the established FDA REMS guidelines will be followed. Eye examinations will be completed within 4 weeks after randomization (Arm A) and then every three months while the subject is in the double blind phase of the study. The eye exams will include: visual acuity, pupillary reaction and dilated funduscopy examination. A final eye exam will be completed after the subject has been off study drug for 3-6 months. The final exam will include: visual acuity, pupillary reaction and dilated funduscopy examination.

If the subject continues into the Open-label phase (Arm B) of the study and remains on vigabatrin, the REMS guidelines will be followed as long as they are treated with vigabatrin. A final eye exam will be completed once they have been off vigabatrin 3-6 months in the Open label phase of the study. The final exam will include: visual acuity, pupillary reaction and dilated funduscopy examination with fundus photography.

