If the subject remains in Arm C (seizure free and Normal EEG) they will have a baseline eye exam within 4 weeks of the initial enrollment in the study. A repeat eye exam will be done at 12 months of age, 24 months of age and 36 months of age.

If at any time during the study the ophthalmologist detects visual changes in the subject, they will contact the site PI directly. At that point, the site PI and ophthalmologist will discuss and recommend further ophthalmologic assessments such as Pediatric optical coherence tomography (OCT) under anesthesia and fundus photography. The parents/LAR, examining ophthalmologist, site PI, and NIH DSMB will review the ophthalmologic examination results and consider all options including the decision to withdraw from the study at that point.

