Additional developmental measures and ASD Risk: The sub-scores on the Bayley-III and the composite score estimated using Hotelling’s  $T^2$ . The power for this endpoint will vary, but is expected to be similar to the primary. In the children with Pervasive Developmental Disorders, the effect sizes versus normal matched controls were 1.77, 1.67, 1.17 and 1.33 for the Receptive communication, Expressive Communication, Fine and gross motor sub-scores respectively. The ADOS2 will be completed at 24 and 36 months of age as a neurodevelopmental assessment for symptoms of ASD. The results from Study Arm A (seizure free, no treatment), Arm B (VGB versus. Placebo), and subjects with electrographic seizures at baseline EEG who move directly into Open Label treatment will be compared increasing our power to assess differences (Figure1).

Determination of vigabatrin safety as a preventative treatment for clinical seizures in infants with TSC will be assessed using comparison between the treatment groups and as a summary of exposure time on the drug. The outcome measure will be percentage of patients in each group (vigabatrin early treatment vs. vigabatrin delayed treatment) with treatment associated adverse events (AEs), serious adverse events (SAEs), and risk evaluation and mitigation strategy (REMS) measures. Treatment related AEs and SAEs will be monitored and tabulated. Given the expectation that the delayed group will cross-over to active treatment sooner than the early treatment group, adverse events will be characterized using life table approaches to ensure adjustment for exposure time. Thus, counts of individuals with AEs, total number of specific AEs and rate per months of follow-up will all be provided and assessed for any differences and for the safety population (early plus late on person years of exposure basis). Events of specific interest and risk evaluation and mitigation strategy (REMS) measures will be compared, including any and all ophthalmologic problems that may arise. Data from the negative control group (estimated to be approximately 15-20 patients) will also be used to compare the occurrence of AEs and SAEs.

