1. Follow up eye exams will be completed within 4 weeks after randomized to vigabatrin or placebo and then every 3 months. A final eye exam will be completed after subject has been off study drug for 3-6 month as per the REMS recommendations. For those patients who come off Vigabatrin at 24 months they will have to have final eye exam between 27-30 months of age.
2. Biomarker samples will be collected at each subject's enrollment, subject randomization to vigabatrin or placebo, clinical seizures onset, and a final sample after 3 months of seizure control after randomization in Arm B or 3 months of uncontrolled seizures in the open label phase of the study.
3. Bayley III (Social-Emotional and Adaptive Behavior Questionnaire) will be completed at 6 month visit and the Bayley Scales of Infant and Toddler Development, Third Edition (Bayley-III) will be completed at 12, 24 and 36 months of age.

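### Ophthalmologic adverse events in the untreated negative-control group (Arm C) are sought at yearly exams, against 3-monthly in treated children, and the planned exposure-time adjustment does not correct that supplementary comparison

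*Combined protocol and SAP*

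**What the plan says.** The safety analysis is described in the Combined protocol and SAP, under Analyses, in the text that follows the heading Additional developmental measures and ASD Risk. The stated outcome is the percentage of early- and delayed-treatment children with treatment-associated AEs, SAEs and REMS measures. Life-table methods and rates per month of follow-up are to adjust for exposure time. Events of specific interest and REMS measures are to be compared, and ophthalmologic problems of any kind are included there. The next sentence brings in Arm C: "Data from the negative control group (estimated to be approximately 15-20 patients) will also be used to compare the occurrence of AEs and SAEs".

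The eye-exam schedules are under Ophthalmologic Assessments and in the footnotes to Appendix 2:

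- **Arm A, vigabatrin and placebo alike:** "within 4 weeks after randomized to vigabatrin or placebo and then every 3 months" (Table 1, footnote 1). The body text agrees: "then every three months while the subject is in the double blind phase of the study".
- **Arm B, open label:** "the REMS guidelines will be followed as long as they are treated with vigabatrin". The section describes the REMS programme as including "recommended ophthalmologic evaluations every 3 months".
- **Children who stop vigabatrin at 24 months:** "they will have to have final eye exam between 27-30 months of age".
- **Arm C, never randomized and never treated:** a baseline exam, and then "A repeat eye exam will be done at 12 months of age, 24 months of age and 36 months of age".

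The analysis text does not mention the difference in the number of exams.

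**The concern.** An eye finding that causes no obvious symptom in an infant is recorded only if somebody examines the child. A group examined four times a year will yield more recorded findings than one examined once a year, even if the drug does nothing. Dividing by months of follow-up does not help, because exams per month is the quantity that differs.

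Visual toxicity is the main side-effect concern that the background section names for vigabatrin, and confirming safety is secondary objective 3. The sample-size section assumes that 22 of 24 placebo children will have a seizure, and such children move to open-label vigabatrin. Drug-free placebo time will therefore shrink, which leaves Arm C as the main never-exposed reference. The background on vision testing also gives reason to expect incidental findings: it reports afferent visual abnormalities at baseline in 20-40% of patients considered appropriate for vigabatrin. In this age group acuity is assessed qualitatively and depends on the child's cooperation.

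**Working it through.** The plan states no exam ratio, ophthalmologic event rate or power for the Arm C comparison, so there is no figure of its own to reproduce.

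**Step 1. Scheduled exams after baseline.** For Arm A, I count the first exam 1 month after randomization and then one every 3 months. Age at randomization is an assumption. For Arm C, I count the exams at 12, 24 and 36 months that fall after that age.

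| Age at randomization | Arm A exams to 24 months | Arm C exams to 24 months | Ratio |
|---|---|---|---|
| 3 months | 7 | 2 | 3.5 |
| 6 months | 6 | 2 | 3.0 |
| 9 months | 5 | 2 | 2.5 |
| 12 months | 4 | 1 | 4.0 |
| 15 months | 3 | 1 | 3.0 |

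Over 36 months the ratio depends on whether the drug continues:

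- Drug stopped at 24 months, with one final off-drug exam: 2.0 to 2.7. Randomized at 6 months, 7 / 3 = 2.3.
- Vigabatrin continued to 36 months: 3.0 to 4.0. Randomized at 6 months, 10 / 3 = 3.3.
- Vigabatrin versus placebo within the blinded phase: 1.0.

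The overall range against Arm C is 2 to 4. While on treatment the rate ratio is (12/3) / (12/12) = 4.

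**Step 2. Incidental findings with no drug effect.** Let q be the chance of a recorded finding per exam, taken as independent between exams (assumption). Then P(at least one in k exams) = 1 - (1 - q)^k. To 24 months, with k = 5 to 7 in Arm A and k = 2 in Arm C:

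- q = 2%: Arm A 1 - 0.98^5 = 9.6% to 1 - 0.98^7 = 13.2%; Arm C 1 - 0.98^2 = 4.0%.
- q = 5%: Arm A 1 - 0.95^5 = 22.6% to 1 - 0.95^7 = 30.2%; Arm C 1 - 0.95^2 = 9.8%.

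**Step 3. Which findings are affected.** For a finding that lasts d months, the chance that a scheduled exam catches it is about min(1, d / interval).

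- d = 3: 1 versus 3/12 = 0.25, a ratio of 4. The ratio is also 4 for shorter findings.
- d = 6: 1 versus 6/12 = 0.5, a ratio of 2.
- d = 12 or more: 1 versus 1, a ratio of 1.

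A persistent defect with onset before 24 months is found in both groups by the last exam, so the ever-affected percentage is not inflated. Only the date of detection moves: the mean delay is half the interval, about 1.5 months against 6.

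**Step 4. Chance of a spurious difference.** This is the probability that a two-sided Fisher test at 0.05 shows more affected children among 24 treated than among 15-20 in Arm C, with 7 versus 3 exams to 36 months and no drug effect. The plan names no test for this comparison, so Fisher's is an assumption.

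| q per exam | Treated | Arm C | Treated vs Arm C, false signal | Vigabatrin vs placebo, 24 each, same schedule |
|---|---|---|---|---|
| 2% | 13.2% | 5.9% | 1.3-3.0% | 1.1% |
| 5% | 30.2% | 14.3% | 12.5-18.2% | 1.3% |
| 10% | 52.2% | 27.1% | 31.5-32.9% | 1.5% |

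**The case against.** The strongest counter-argument is that the plan does not depend on Arm C. The stated safety outcome is early versus delayed treatment, and both randomized groups have the same exam schedule in the blinded phase. An excess produced by looking more often would appear under placebo too, which would argue against a drug effect. No test, threshold or go decision is attached to the Arm C comparison. All of this stands. A reader might infer from the schedules that eye events will be put down to vigabatrin simply because treated children are examined more often. The documents do not support that, because the blinded placebo group is a matched control.

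Four further points deserve weight.

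- The Arm C sentence names AEs and SAEs, while ophthalmologic problems and REMS measures are in the sentence before it. An Arm C comparison of eye events is the natural reading, since nothing excludes them, but it is not spelled out.
- Adverse Event Reporting says that changes in health status and disease progression will not be evaluated as adverse events. This may keep some TSC-related eye findings out of the AE count.
- The per-exam rates are assumptions. At 2% the false-signal probability is small.
- The exam counts assume 3-monthly exams to 24 months. Open-label vigabatrin may be tapered, and such children would then have fewer.

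A reader might also see a contradiction with the statement under Ophthalmologic Assessments that all subjects follow a standard protocol. That section goes on to set arm-specific schedules, and the vision-testing background speaks of standardized evaluation across sites. Standard can mean uniform procedure, so a contradiction is not established.

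**Conclusion.** The point holds for one supplementary comparison. Carried out as written, the Arm C comparison of ophthalmologic events would set treated children with 2 to 4 times as many scheduled exams against Arm C, and no planned adjustment addresses this. The bias is towards more events in treated children. It affects transient and incidental findings, event counts, monthly rates and time to detection.

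It does not affect blinded vigabatrin versus placebo, nor the ever-affected percentage for persistent defects with onset before 24 months. After the blinded phase, equal schedules between the randomized groups are no longer assured, because exams then depend on whether the child remains on vigabatrin.

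The size cannot be fixed from the documents. It rests on the assumed per-exam rate, independence between exams and the assumed age at randomization. At 2-5% per exam, about 10-30% of Arm A against 4-10% of Arm C would have a finding by 24 months with no drug effect. This is a modest but foreseeable flaw that can be removed before unblinding.

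**What to change.** Change the analysis wording and leave the exam schedules as they are:

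1. State that attribution of ophthalmologic events rests on vigabatrin versus placebo in the blinded phase, using all 3-monthly data.
2. State whether ophthalmologic events are part of the Arm C comparison. If they are, limit it to findings at baseline and at the exams nearest 12 and 24 months. Use 36 months only where both groups were examined at that age: children who stop at 24 months have their final exam at 27-30 months, and Table 1 marks no eye exam at 36 months. Alternatively, report findings per examination.
3. Report persistent defects separately from transient or incidental findings, and describe the Arm C comparison as non-randomized.

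The cost is a few sentences of SAP text, and interim 3-monthly findings are left out of the age-matched Arm C comparison. The change does not remove confounding: Arm C is by definition free of EEG abnormality and seizures, so the comparison remains descriptive.

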### **Secondary Study Objectives:**

- 1) Determine the effectiveness of early versus delayed treatment with vigabatrin in clinical seizure prevention. The outcome measure will be time to first clinical seizure following randomization. The prevalence of drug-resistant epilepsy will be assessed at 24 months for each group (vigabatrin early treatment vs. vigabatrin delayed treatment).
- 2) Determine the impact of early versus late treatment on the other components of the Bayley-III (receptive communication, expressive communication, fine and gross motor skills) and risk of autism spectrum disorders (ASD). The primary outcome measures for this objective will be subdomain scores of the Bayley-III, Vineland-II (Survey Interview Form), Beery Visual Motor Integration (VMI), and ADOS2 at 24 months. Additional exploratory analysis will be completed at 36 months to assess changes observed at 24 months are consistent with those seen at 36 months and indicative of long-term outcome. At 36 months of age subjects will also complete the Peabody Picture Vocabulary Test (PPVT). During the COVID-19 Pandemic in order to minimize the risk of infection to observer and infant until the completion of the study the Brief Observation of Symptoms of Autism (BOSA) will be administered at 24- and 36-month visits. Additionally, the ADI-R will be administered at the 36-month visit.
- 3) Confirm vigabatrin safety as a preventative treatment for clinical seizures in infants with TSC. The outcome measure will be percentage of patients in each group (vigabatrin early treatment vs. vigabatrin delayed treatment) with treatment associated adverse events (AEs), serious adverse events (SAEs), and risk evaluation and mitigation strategy (REMS) measures.
- 4) Confirm of the feasibility of using EEG biomarkers to identify TSC infants at risk for developing epilepsy. The outcome measure will be the sensitivity and specificity of EEG epileptiform activity in predicting epilepsy outcomes at 24 months within treatment groups.

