For the accurate identification of clinical seizures, parents and caregivers will review a seizure recognition video at the time of study enrollment and retain it as a reference throughout the study. They will also be encouraged to video any suspicious events during the study period for review by clinicians of the investigation team. If at any point during the study the subject is suspected of having a clinical seizure, the parents/caregiver will be instructed to contact their site's study coordinator. The subject will be seen as soon as possible for a study visit and a video EEG will be completed for confirmation of clinical or electrographic seizure onset. Those subjects with either a documented clinical seizure on video or evidence of an electrographic seizure on video EEG will be transitioned to the Open-Label treatment phase.

At the emergence of abnormal epileptiform activity (*i.e.* sharp waves, spikes or polyspikes, spike and wave discharges, classic or modified hypsarrhythmia) prior to the onset of the first clinical or electrographic seizure, subjects will enter the protocol blinded-treatment phase (Arm A). Emergence of these specific, predetermined EEG biomarkers detected by video EEG will lead to a 1:1 randomization with vigabatrin or placebo. The vigabatrin and placebo will be dispensed as a sachet and those subjects randomized to vigabatrin will be titrated up to 100mg/kg/day by 50mg/kg/day every 3 days during the blinded phase of the study. The research pharmacist at each site will be unblinded during this phase of the study and the vigabatrin and placebo sachets doses will be identical in order to maintain the blind.

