If an enrolled subject has an electrographic or clinical seizure(s) prior to randomization and the previous EEG(s) have been normal they will move into the Open label phase of the study (Arm B). If the seizures are not controlled in the Open label phase at the vigabatrin maximum dose of 150mg/kg/day, the investigator may change the antiepileptic medication as clinically warranted to improve seizure control (including tapering off vigabatrin). These subjects will remain in the open arm of the study for the duration of the protocol (36 months).

Patients enrolled without prior clinical seizures but found on first baseline EEG to have electrographic or clinical seizures of which the parent and clinician were previously unaware will exit the PREVeNT trial and begin medical treatment by the site PI based on clinically accepted management guidelines for seizures in TSC infants. Based on the P20-NS080199 study, this group is estimated to be very small (<5%) and will not affect the total number of enrolled patients (N=80) eligible to be randomized to either placebo or vigabatrin treatment.

Enrolled subjects who never develop EEG abnormalities or clinical seizures (ARM C) will remain in the study and continue with regular clinical evaluations, EEG testing, and developmental assessments as scheduled (Table 2). Without EEG change or developing seizures, they will have neither been randomized nor treated with vigabatrin. These patients will serve as a negative control and be key for validating the sensitivity and specificity of EEG biomarkers as predictors of seizure risk and baseline disease characteristics attributable to TSC that are independent of epilepsy and AED treatment (TREATMENT ARM A).

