The deidentified EEG data, without video, will be transferred to IEEG.org managed by the University of Pennsylvania for same day analysis by the blinded primary central EEG reviewer. There will be an assigned back up EEG reader to the primary central EEG reviewer in the rare instance that primary central EEG reviewer is not available. There will be 2 EEG readers ([name] and [name]) throughout the study. Prior to the subject randomization, the EEGs will be read the same day as the EEG is completed by either EEG reader, which will be pre-determined the week prior for any given week, and a CRF report will be generated. Once the subject has been randomized the EEGs will be read by both readers within 14 days of the EEG being completed. The primary central EEG reviewer's interpretation of the EEG and identification of epileptiform activity will determine if the subject will be placed in Arm A for treatment randomization to vigabatrin or placebo.

The Central EEG reviewer's interpretation will be communicated back to each site. The primary central EEG reviewer will be available to each site as needed for clarification or any discrepancy of the individual site readers EEG interpretation. Should either the primary central EEG reviewer or the backup EEG reader be uncertain of epileptiform discharges in rare cases, these two readers will consult each other and reach a consensus.

Video EEG will be viewed digitally in the standard time scale of 30 mm/sec and standard filter settings of 1 Hz low frequency filter (high pass) and 70 Hz high frequency filter (low pass), along with a 60 Hz notched filter. Each video-EEG study will be scored, based on age-appropriate norms, as either: normal or abnormal. Abnormalities will be further characterized in terms of specific background abnormalities (e.g. generalized or focal slowing), epileptiform abnormalities (e.g. focal, multifocal, or generalized spike discharges, electrographic seizures), and presence of hypsarrhythmia. EEG data will be collected using a modified NINDS Common Data Element Epilepsy Tools.

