EEG biomarker feasibility: The outcome measure will be the sensitivity and specificity of EEG epileptiform activity in predicting outcomes at 24 months for each treatment group. To confirm the feasibility of using EEG biomarkers to identify TSC infants at risk for developing epilepsy, sensitivity and specificity of EEG epileptiform activity at each time-point for predicting subsequent development of epilepsy by 24 months of age will be conducted within each treatment arm. Successful treatment in the vigabatrin arm should produce significantly poorer specificity and lower positive predictive value (PPV) by mitigating the predictive power of the EEG epileptiform activity. Exploratory analysis will further evaluate the timing of EEG change with time to seizure onset and type of EEG change with epilepsy type and treatment response as a covariate in the Cox proportional hazards assessment of time to clinical seizure. Additional analysis will evaluate the separate impact of TSC clinical features and concurrent AEDs. Our estimate is that 75% will develop the EEG biomarker prior to clinical seizures, some of the enrolled infants will

develop neither EEG biomarker nor seizures and some will develop seizures prior to being identified with the EEG biomarker or never develop the EEG biomarker despite the onset of clinical seizures. If the incidence of developing the EEG biomarker relative to the incidence of seizures without the EEG biomarker is very low, then the efficacy of treatment would have to be great to warrant the cost of monitoring. Thus, evaluation of this aim will be a tradeoff between biomarker incidences versus the treatment benefit. Descriptive statistics and numbers needed to treat (NNT) will be used to evaluate this endpoint.

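### EEG biomarker accuracy is planned within the randomised arms, where every child is index-EEG positive by design, so index-EEG sensitivity and specificity are fixed in advance

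*Combined protocol and SAP*

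**What the plan says.** Secondary Study Objectives, item 4, sets as outcome the "sensitivity and specificity of EEG epileptiform activity in predicting epilepsy outcomes at 24 months within treatment groups". Under Analyses, the EEG biomarker feasibility paragraph plans this at each time-point and says it "for predicting subsequent development of epilepsy by 24 months of age will be conducted within each treatment arm". It then predicts: "Successful treatment in the vigabatrin arm should produce significantly poorer specificity and lower positive predictive value (PPV".

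The route into the arms is set elsewhere. Protocol description (text after the exclusion criteria): "Emergence of these specific, predetermined EEG biomarkers detected by video EEG will lead to a 1:1 randomization with vigabatrin or placebo". EEG Acquisition and Data Transfer says that the central reader's "identification of epileptiform activity will determine if the subject will be placed in Arm A for treatment randomization to vigabatrin or placebo".

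Children without the biomarker are never randomised. Those who seize after normal EEGs go straight to open-label Arm B. Those with neither EEG change nor seizures form Arm C, which the protocol says will "be key for validating the sensitivity and specificity of EEG biomarkers as predictors of seizure risk". The feasibility paragraph also recognises that "some will develop seizures prior to being identified with the EEG biomarker or never develop the EEG biomarker despite the onset of clinical seizures", and weighs the incidence of such seizures against treatment benefit, using descriptive statistics and numbers needed to treat (NNT).

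**The concern.** Sensitivity and specificity need test-negative children: false negatives for one, true negatives for the other. The design sends both kinds outside the randomised arms, and the stated analysis is confined to those arms. For the EEG that triggers randomisation, two of the three named measures are therefore settled before any data arrive, and the third, PPV, is simply the proportion of the arm with seizures. The predicted fall in specificity on vigabatrin cannot appear for that EEG, because specificity is already zero in both arms or undefined.

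At stake is the evidence for EEG surveillance in asymptomatic infants, which the background section presents as one of the trial's products. The protocol gives Arm C a role in this validation, but the analysis text never puts Arm C, or the children who seize without the biomarker, into an accuracy table.

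**Working it through.** **1. The pilot figures (Study/Background/Rationale).** Stated: sensitivity 73.7%, specificity 100%, PPV 100%, negative predictive value (NPV) 64%. Among integer tables with no false positives and at most 40 infants, one matches: TP 14, FN 5, TN 9, FP 0. Check: 14/19 = 73.7%, 9/9 = 100%, 14/14 = 100%, 9/14 = 64.3%. Half of these 28 infants (5 + 9 = 14) are EEG-negative. Without them sensitivity becomes 14/14 = 100%, and specificity and NPV become 0/0.

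**2. The trial as written, index EEG.** Inputs from the sample-size text: 24 per arm, seizures in 22/24 on placebo (with all expected to seize before the conservative discount) and 5/24 on vigabatrin.

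| Arm | TP | FP | FN | TN | Sensitivity | Specificity | PPV (exact 95% CI) |
|---|---|---|---|---|---|---|---|
| Placebo | 22 | 2 | 0 | 0 | 22/22 = 100% | 0/2 = 0% | 22/24 = 91.7% (73.0-99.0) |
| Vigabatrin | 5 | 19 | 0 | 0 | 5/5 = 100% | 0/19 = 0% | 5/24 = 20.8% (7.1-42.2) |

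If all 24 placebo children seize, placebo specificity is 0/0. NPV is 0/0 in both arms.

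**3. The tables at each time-point.** A randomised child can have had negative EEGs before the index EEG and can have them afterwards, so these tables are not fixed in the same way. They still omit every child who never turned positive, and EEGs after randomisation reflect treatment.

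**4. With the never-randomised children added (illustration).** Placebo children stand for all untreated EEG-positive children. With 1:1 allocation each is weighted by 2, giving TP 44 and FP 4. Assume 30 never randomised (the upper figure in the sample-size text), no dropout, and each such child either in Arm C (TN) or direct-entry Arm B (FN).

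| Arm C (source) | FN | Sensitivity | Specificity | NPV |
|---|---|---|---|---|
| 30 (sample size: all never-randomised are biomarker free) | 0 | 44/44 = 100% | 30/34 = 88.2% | 30/30 = 100% |
| 24 (Vigabatrin and Placebo) | 6 | 44/50 = 88.0% | 24/28 = 85.7% | 24/30 = 80% |
| 15 (low end of 15-20, safety analysis) | 15 | 44/59 = 74.6% | 15/19 = 78.9% | 15/30 = 50% |

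The total is 24 + 24 + 30 = 78, within the expected 75 to 80. With 25 per arm and Arm C of 24, the figures are 88.4% and 85.2%.

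The feasibility paragraph also says "Our estimate is that 75% will develop the EEG biomarker prior to clinical seizures". If that means 60 of 80 randomised (an assumption), 20 are not. At 30 per arm the weighted counts are TP 55 and FP 5. Arm C of 20 gives 55/55 = 100% and 20/25 = 80%. Arm C of 15 gives 55/60 = 91.7% and 15/20 = 75%.

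**5. Precision.** On the logit scale, SE = sqrt(1/TP + 1/FN) for sensitivity and sqrt(1/FP + 1/TN) for specificity, using unweighted counts. For Arm C of 24:
- Sensitivity: ln(44/6) = 1.992, SE = sqrt(1/22 + 1/6) = 0.461, 95% CI 75-95%.
- Specificity: ln(24/4) = 1.792, SE = sqrt(1/2 + 1/24) = 0.736, 95% CI 59-96%.

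If between 1 and 4 of the 24 placebo children stay seizure free, specificity runs from 24/26 = 92% to 24/32 = 75%.

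**6. Pooling both arms without adjustment.** With Arm C of 24, FP = 2 + 19 = 21 and specificity is 24/45 = 53.3%, because seizures that vigabatrin prevented count as false positives.

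**The case against.** The degenerate table is not all that is planned. The text asks for accuracy at each time-point, and those tables can hold negatives. This stands: the fixed values apply to the index EEG only. A reader might infer that objective 4 can yield nothing but PPV. The documents do not support that; the time-point results are selected and treatment-affected, hence limited, but not empty.

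A reader might also infer that the plan means to ignore EEG-negative children. It does not. Arm C has a stated validation role, seizures without the biomarker enter the descriptive trade-off, and Additional measures and analyses considerations lists a normal-EEG, seizure-free, never-randomised group. What is missing is a statement of how these children enter the sensitivity and specificity calculation.

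Could treatment arm mean Arms A, B and C? The objectives define the groups as early versus delayed vigabatrin. Even on the wider reading, Arm C holds only true negatives and the direct entrants to Arm B are all false negatives, so separate tables would still fail.

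NPV is not a planned outcome of objective 4, so its absence is no defect. The whole-cohort figures do not measure the size of the problem either: they rest on inconsistent statements of Arm C's size, and the 15 false negatives in the lowest row are stated nowhere in the plan.

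**Conclusion.** The within-arm accuracy analysis is wrong as written for the index EEG. Sensitivity is 100% and specificity 0% or undefined by design, whatever the biomarker's merit. PPV is free to vary (91.7% against 20.8% at the plan's rates), but the difference restates the seizure comparison. The predicted loss of specificity on vigabatrin cannot be seen for that EEG. These results follow from the randomisation rule; only the PPV values depend on the assumed seizure rates.

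The problem lies in the analysis specification and not in data collection, since Arm C and direct-entry Arm B children are followed to 36 months. It should be settled before unblinding, because the choice of population and weighting moves the answer: with Arm C of 24, specificity is 85.7% under allocation weighting and 53.3% if both arms are pooled unadjusted. The randomised seizure and Bayley-III comparisons are untouched.

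**What to change.** In Secondary Study Objectives, item 4, and in the EEG biomarker feasibility paragraph:

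- Define the index test as epileptiform EEG before the first seizure.
- Report PPV by arm with exact confidence intervals.
- Estimate sensitivity and specificity in children untreated before their first seizure: the placebo arm weighted by the inverse of its observed allocation fraction (about 2), plus children entering Arm B directly, plus Arm C. Use confidence intervals that account for the weighting. Add NPV if a comparison with the pilot is wanted.
- Keep the within-arm results at each time-point as descriptive.
- State that the two arms will not be pooled without adjustment.

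Separately, reconcile the group described in Additional measures and analyses considerations as having electrographic seizures at baseline with the rule after the exclusion criteria that such children leave the study. Say whether the 28-30 never-randomised children counted there include direct entrants to Arm B, and reconcile the stated sizes of Arm C.

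The cost is SAP wording and one weighted two-by-two analysis of data already collected. The downside is precision: specificity rests on the few seizure-free placebo children, with intervals of 64-97%, 59-96% and 46-94% for Arm C of 30, 24 and 15 in the illustration.
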